15. BIBLIOGRAPHY							

EXPERIMENTAL SCHEMA

Figure 1: Standardized treatment protocol including study inclusion criteria and discharge checklist.

Discharge

Follow up within 30

days in clinic or via

phone or mail

PROTOCOL SIGNATURE

I confirm that I have read and understood this protocol, and I will conduct the study as outlined herein and according to the ethical principles stated in the latest version of the Declaration of Helsinki, the applicable ICH guidelines for good clinical practice, and the applicable laws and regulations of the federal government. I will promptly submit the protocol to the IRB for review and approval. Once the protocol has been approved by the IRB, I understand that any modifications made during the course of the study must first be approved by the IRB prior to implementation except when such modification is made to remove an immediate hazard to the subject.

I will provide copies of the protocol and all pertinent information to all individuals responsible to me who assist in the conduct of this study. I will discuss this material with them to ensure that they are fully informed regarding the study treatment, the conduct of the study, and the obligations of confidentiality.

Signature of Principal Investigator

Date

[name]

Principal Investigator Name (Print)

Johns Hopkins All Children's Hospital

Name of Institution

STUDY SUMMARY

Title	Antibiotic Instillation in Acute Complex Appendicitis for
	Prevention of Deep Space Surgical Site Infections
Short Title	Antibiotic Instillation in Appendicitis
IND	IND
Phase	Pilot Phase 2
Design	Randomized single blind control study
Study Duration	1 year
Study Center(s)	Single-center
Objectives	The primary objective is to evaluate the feasibility and safety of the use of antibiotic instillation in the treatment of complex acute appendicitis measured by enrollment rates and ability to complete all study tasks. Secondary objectives are to examine the rate of intra-abdominal abscess formation and post-operative length of stay following treatment of complex appendicitis in the setting of appendectomy with intra-operative suction alone compared to suction with intra-peritoneal antibiotic instillation
Number of Participants	A total of 36 patients will be randomized to two groups in this pilot study

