1 OBJECTIVES

1.1.1 Primary objective

To evaluate the feasibility and safety of the use of antibiotic solution instillation following intraoperative diagnosis of complex appendicitis. We will determine feasibility by the percentage of eligible participants who (1) agree to participate, and (2) complete all intervention sessions and measurement time points. Safety will be evaluated by adverse events associated with the use of intra-peritoneal antibiotic instillation for the treatment of peritonitis caused by complex appendicitis.

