Study participants will be randomized in a 1:1 ratio using permuted blocks of 4 and 6 using a computer-generated randomization scheme. The treatment category assignments will be placed in consecutive numbered envelopes concealed from study staff until randomization. In the operating room, once the patient is diagnosed with complicated appendicitis, then the next sequential envelope will be opened and the patient will be assigned to that treatment arm. The surgeon and team administering the treatment will not be blinded; however, patients, their families, and hospital caregivers outside of the operating room will be blinded to the treatment. Post-operative protocols will be the same for both groups and includes continuation of intravenous antibiotics (Study Schema, and Fig 1). Once complex appendicitis is diagnosed, and a successful appendectomy occurs, then the patient will be transitioned to intravenous ceftriaxone (50mg/kg/day, maximum 2g daily) and metronidazole (30mg/kg/day) post-operatively. Both study groups will receive a minimum additional 48 hours of intravenous ceftriaxone and metronidazole, as per our weight based current standard of care. Patient status and post-operative recovery back to baseline will dictate discharge or continued hospitalization. Pending their clinical course, patients will be either transitioned to broadspectrum oral antibiotics or continued on intravenous ceftriaxone and metronidazole until their discharge from the hospital. Our standardized discharge criteria includes: temperature less than 38.5°C for the previous 24 hours, improved abdominal pain without the use of narcotics, and tolerance of enteral intake. Once these criteria have been met, and at the surgeon's discretion, the patient will be discharged home with routine follow-up (either a clinic visit, telemedicine visit, or a phone call) within 30 days after surgery.

If the patient remains hospitalized on post-operative day 7 (plus or minus 1 day) related to postoperative care of complicated appendicitis, and does not meet discharge criteria as listed, then they will undergo subsequent imaging studies (abdominal ultrasound or CT abdomen-pelvis) to evaluate for intra-abdominal abscess or phlegmon. If patients are found to have an abscess or phlegmon, they will continue to receive ongoing antibiotic treatment with or without percutaneous aspiration and/or drainage at the discretion of the surgeon and interventional radiologist.

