4.1 Number of Participants

Thirty-six patients will be enrolled. We will screen approximately 400 patients within the eighteen-month period.

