4.3 Study Duration

We will begin screening patients after IRB approval of our pilot study. We will continue screening and inclusion in the trial until enrollment is met. We suspect this will take approximately eighteen months. The duration of participation will be approximately 30-days from the time of appendectomy. We will continue our pilot study until we have enrolled a total of 36 patients.

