12 STATISTICAL CONSIDERATIONS

A JHACH database manager will create a REDCap database for the study on the passwordprotected JHACH secure network. A Pediatric Surgery Research Fellow will enter data, and the Principal Investigator will check the initial data on six participants for accuracy and completeness and spot-check the data entry independently at least once a month.

All data will be checked for completeness and consistency at the end of the study. Tabular and graphical methods will be used to explore the distribution of the variables. Baseline demographic and clinical characteristics will be summarized using descriptive statistics for continuous (mean, standard deviation, median, range) and categorical variables (counts, percentages). Baseline differences between the groups will be evaluated using independent t-test or

Mann Whitney U test for continuous variables as appropriate, and Chi-squared or Fisher's exact test for categorical variables as appropriate. All statistical analyses will be performed with SAS v 9.4 or a newer version.

Analysis for Aim 1.

The primary aim of this study is to determine the feasibility and safety of the use of antibiotic solution instillation following intraoperative diagnosis of complex appendicitis. We will determine feasibility by the percentage of eligible participants who (1) agree to participate, and (2) complete all intervention sessions and measurement time points. Safety will be determined by adverse events associated with the use of intra-peritoneal antibiotic instillation for the treatment of peritonitis caused by complex appendicitis. For feasibility, we will report the proportions with corresponding 95% confidence intervals for eligibility, recruitment, enrollment, withdrawals and drop outs, and study completion. We will also collect information on barriers and issues of implementation. The study will be deemed feasible if >50% of potential participants agree to participate and at least 75% of them complete all measurement time points. These benchmarks are based on a previous similar study completed in this population. [29]. For safety we will report the incidence of adverse effect with the corresponding 95% confidence interval.

Analyses for secondary aims

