The primary aim of this study is to assess feasibility of the proposed intervention to inform a future larger randomized controlled trial. Therefore, the sample size is not based on a power analysis. A sample size of 36 participants (18 intervention and 18 control) is appropriate to provide feasibility data that will help refine our intervention and measurements for a future larger study.[30] This sample size will allow us to estimate a conservative participation of 70% with a confidence interval of 53-87%. In a similar study conducted by the PI previously, 85% of recruited families consented to randomization and >93% of those families completed all study assessments.

Based on current estimates in our institution, we anticipate 350 appendectomies to be performed each year. Assuming the average documented 20% perforation rate, we anticipate 70 appendectomies for complicated appendicitis each year. Therefore, we will have an eligible pool of 70 patients with intra-operatively diagnosed complicated appendicitis. [29]

Study Monitoring and stopping rules:

All patients will be monitored in the post-operative period, particularly the first 48 hours following surgery. Given the study involves a single dose of intra-peritoneal antibiotic instillation any drug side effects will likely occur within the first 12 hours of treatment. At any time in the study, if a patient suffers an adverse event secondary to intra-peritoneal antibiotic instillation, all study activity will be suspended until a full investigation is completed. The study will only be reinstated after consultation with the Johns Hopkins All Children's Hospital IRB. Patients with severe allergies to cephalosporins or penicillin will be excluded from the study.

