14 ETHICAL AND REGULATORY CONSIDERATIONS

14.1 Informed consent

Informed consent is obtained from all research participants and/or the legal guardian prior to performing any study procedures using the most recent IRB approved version.

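### The 53-87% interval for 70% participation is tied to the 36 randomized patients, who have all already consented; it belongs on a denominator that includes families who decline

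*Combined protocol and SAP*

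**What the plan says.** Section 1.1.1 and the Aim 1 analysis in Section 12 define the measure in the same words: "We will determine feasibility by the percentage of eligible participants who (1) agree to participate". The decision rule, also under Aim 1, uses a different term. The study will be "deemed feasible if >50% of potential participants agree to participate and at least 75% of them complete all measurement time points". Aim 1 also promises 95% confidence intervals for eligibility, recruitment, enrollment, withdrawal and completion proportions.

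The sample size justification in Section 12 gives 36 participants (18 intervention, 18 control) and continues: "This sample size will allow us to estimate a conservative participation of 70% with a confidence interval of 53-87" percent. The next sentence cites 85% consent to randomization and more than 93% completion in a similar earlier study.

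Other sections establish who the 36 are. The Study Summary says "A total of 36 patients will be randomized to two groups in this pilot study". Section 14.1 says "Informed consent is obtained from all research participants and/or the legal guardian prior to performing any study procedures". Section 4 places randomization in the operating room: "once the patient is diagnosed with complicated appendicitis, then the next sequential envelope will be opened". Section 6.1 classes patients who consent but are not randomized as screen failures. Section 4.3 sets the end of recruitment: "We will continue our pilot study until we have enrolled a total of 36 patients". On the wider population, Section 4.1 says "We will screen approximately 400 patients within the eighteen-month period".

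**The concern.** A participation rate needs refusers in its denominator. The 36 contain none, because each patient consented before being randomized. A 70% rate cannot be estimated from a group in which agreement is 100% by design, so the interval is attached to a quantity that 36 does not determine.

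The plan does not supply the right denominator either. *Eligible* has two senses. Sections 5.1 and 5.2 and the annual pool of 70 in Section 12 make complex disease part of eligibility. Section 4 and the opening of Section 5 apply the word to all children with acute appendicitis having urgent appendectomy, who are approached before the operative diagnosis is known. *Potential participants*, in the decision rule, is not defined.

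Feasibility is the primary aim, and this is the only precision figure in its sample size justification. The observed rate will be judged against the >50% benchmark and will inform a larger trial, so two analysts should not be able to compute it on different populations.

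**Working it through.** **Inputs.** From Section 12: participation 70%; n = 36; 95% level (stated for the Aim 1 proportions, not repeated beside 53-87%); complex disease 20%; earlier consent rate 85%; completion benchmark 75%. From Section 4.1: about 400 screened.

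**1. The plan's own figure.** With p = 0.70 and n = 36, the standard error is sqrt(0.21/36) = 0.0764.
- Plain Wald: 0.70 ± 1.96 × 0.0764 = 55.0-85.0%.
- Wald with continuity correction (add 1/72 = 0.0139): 53.6-86.4%.
- Continuity correction with a t quantile on 35 degrees of freedom: 53.1-86.9%, which rounds to 53-87%.

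The stated interval can be obtained at n = 36, but the method is not given. Plain Wald at n = 28 also gives 53.0-87.0%. The link to 36 therefore rests on the words *This sample size*, not on the arithmetic.

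**2. Agreement among the 36.** Consent comes before any study procedure, randomization follows in the operating room, and consenters who are not randomized fall outside the 36. Agreement is 36/36 = 100%.

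**3. Could 70% be a completion rate?** The 36 would then be the right denominator. But 70% is below the plan's 75% completion benchmark, and the sentence that follows compares it with an 85% consent rate. The text reads as consent.

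**4. Denominators that include refusers** (95% Wald, 0.70 ± 1.96 × sqrt(0.21/n)).

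| Denominator | n | 95% CI | Half-width, points |
|---|---|---|---|
| Stated in the plan | 36 | 53-87% | 17 |
| Complex cases only | 36/0.70 ≈ 51 | 57-83% | 12.6 |
| All families approached | 36/(0.70 × 0.20) ≈ 257 | 64-76% | 5.6 |
| All 400 screened, if all are approached | 400 | 65.5-74.5% | 4.5 |

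The figures 51 and 257 assume no losses other than refusal and, for 257, simple disease. At 85% consent, the number approached would be 36/(0.85 × 0.20) ≈ 212.

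**5. What 36 can describe.** Under the all-approached reading, consenters number 0.70 × 257 ≈ 180, of whom 36 (20%) are randomized and the rest are screen failures. A 75% completion benchmark is workable only among the 36. Exact (Clopper-Pearson) 95% intervals are:
- 27/36 (75%): 57.8-87.9%
- 33/36 (92%): 77.5-98.2%

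**The case against.** The strongest reply is that nothing turns on the sentence. The plan says the sample size is not power-based and supports it with a pilot-size reference. The error runs in the safe direction, and the Aim 1 analysis already promises 95% intervals on the observed proportions, so the final report can carry the real precision. This stands, and it keeps the point minor. It does not make the stated precision correct or settle which population the rate will be computed on.

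It is also fair to say that the replacement figures depend on assumptions. They need exactly 70% consent, 20% complex disease and no other losses, while Section 5 has further exclusions. Because recruitment stops at 36 randomized, the number approached is random. The figures are therefore illustrations.

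Three stronger readings are tempting, and the documents do not support them.
- A reader might infer that the plan names no denominator. Section 12 does describe one, in two terms; what is missing is a definition and a size.
- A reader might infer that 53-87% is an arithmetic error because plain Wald gives 55-85%. The method is unstated and another standard variant reproduces the figure.
- A reader might infer that screening 400 contradicts randomizing 36, since 400 × 0.70 × 0.20 = 56. Not everyone screened need be eligible and approached, and recruitment stops at 36, so the two figures can both hold.

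**Conclusion.** The precision statement is wrong as written, and the point is minor. The 36 randomized patients cannot be the denominator for participation, and the 17-point half-width is not the precision of that estimate. On denominators that include refusers, the half-width at 70% is about 4.5 to 12.6 points; it is 5.6 points if all families approached are counted. At 70%, the lower limit exceeds 50% in every case (53 stated; 57, 64 or 65.5 recomputed). It would be wrong to conclude that the pilot is too small or that its participation criterion is at risk.

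That the 36 all consented follows directly from the text. The sizes rest on the assumed 70% consent and 20% complex disease with no other losses. The conclusion that the interval was computed for 36 rests on the plan's wording.

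**What to change.** 1. **Section 12, Aim 1.** Define the participation denominator once, for both the percentage and the >50% criterion: all families approached for consent whose child meets the criteria that can be assessed before surgery. This denominator is observable under the plan as written. State that the 75% completion criterion is judged among the 36 randomized.
2. **Section 12, sample size justification.** Replace the participation interval with an illustrative one that gives its method and assumptions. For example: about 257 families approached, at 70% consent and 20% complex disease with no other losses, give a 95% Wald interval of about 64-76%. Add that about 212 would be approached if consent is 85%, and that the interval at 70% is 65.5-74.5% if all 400 screened are approached.
3. **Same paragraph.** Attach the precision of n = 36 to completion: exact 95% interval 58-88% for 27/36 and 78-98% for 33/36.

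The cost is small edits to two parts of Section 12. Sample size and benchmarks do not change. A complex-only denominator (about 51, interval 57-83%) should be used only if operative findings can be obtained for families who decline; the plan does not describe collecting them.

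### The 53-87% interval quoted for 70% participation is not what the usual 95% methods give at n=36 (Wald gives 55-85%), and the plan states neither method nor level for it

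*Combined protocol and SAP*

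**What the plan says.** All of this is in Section 12, Statistical Considerations.

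- Sample size: "A sample size of 36 participants (18 intervention and 18 control) is appropriate to provide feasibility data". A published rule of thumb for pilot studies is cited in support.
- Precision, in the next sentence: "This sample size will allow us to estimate a conservative participation of 70% with a confidence interval of 53-87" percent. That sentence names no confidence level, no interval method and no number other than the 36 just given.
- Power: "Therefore, the sample size is not based on a power analysis".
- Level for the Aim 1 results: "we will report the proportions with corresponding 95% confidence intervals for eligibility, recruitment, enrollment, withdrawals and drop outs, and study completion".
- Definition of the feasibility measures: "We will determine feasibility by the percentage of eligible participants who (1) agree to participate, and (2) complete all intervention sessions and measurement time points".
- Success rule: "The study will be deemed feasible if >50% of potential participants agree to participate and at least 75% of them complete all measurement time points".

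**The concern.** Apart from the cited rule of thumb, the 53-87% interval is the only numerical support for 36 participants and the only precision figure in the plan. A reader should be able to rebuild it from the stated n and level. The natural attempt, a symmetric 95% interval around 70% with n=36, gives a narrower result.

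Two things are at stake, both modest. First, a reader cannot tell whether the figure is a slip, an unusual but defensible formula, or a calculation for some other number of participants. Second, the pilot is meant to inform the design of a larger trial, so whoever plans that trial needs to know what the figure describes. This is harder because the sentence speaks of participation, whose denominator is not the 36.

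**Working it through.** **Inputs.** n = 36 and p = 0.70, with a stated interval of 53-87% (half-width 17 points), from the sample size paragraph. The 95% two-sided level is taken from the Aim 1 analysis, because the precision sentence gives none.

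**Step 1: try to reproduce the plan's figure.** The interval is symmetric about 70%, so start with Wald, p ± z·√(p(1−p)/n):

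0.70 ± 1.96·√(0.21/36) = 0.70 ± 0.150, that is 55.0-85.0%. The plan's figure is not reproduced.

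**Step 2: other usual 95% methods at n=36.** Since 70% of 36 is 25.2, the nearest whole count is 25 (69.4%).

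| Method | 95% interval (%) |
|---|---|
| Wald, t quantile | 54.5-85.5 |
| Wald, n−1 variance | 54.8-85.2 |
| Wald, t quantile and n−1 variance | 54.3-85.7 |
| Wald, continuity correction 1/(2n) | 53.6-86.4 |
| Exact (Clopper-Pearson), 25/36 | 51.9-83.7 |
| Wilson, 25/36 | 53.1-82.0 |
| Agresti-Coull, 25/36 | 53.0-82.1 |
| Jeffreys, 25/36 | 53.4-82.6 |

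None rounds to 53-87%. Several share the lower limit of 53, but their upper limits are 82 or 83. Using 26/36 does not help (exact 54.8-85.8, Wilson 56.0-84.2).

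**Step 3: what does print 53-87%.**

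- Continuity correction with n−1 variance, n=36: 0.70 ± [1.96·√(0.21/35) + 1/72] = 53.4-86.6%.
- Continuity correction with a t quantile (35 df), n=36: 53.1-86.9%.
- Continuity correction with both, n=36: 52.9-87.1%.
- Plain Wald with a smaller n: solving 1.96·√(0.21/n) = 0.17 gives n = 27.9. The limits round to 53-87% at n=27 (52.7-87.3), n=28 (53.0-87.0) and n=29 (53.3-86.7).
- Continuity-corrected Wald with n from 32 to 35.
- Plain Wald at n=36 with a higher level: z = 0.17/√(0.21/36) = 2.23, about 97.4% confidence.

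The plan states none of these choices.

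**Step 4: size of the gap.** Against plain Wald, each limit differs by 2 points (53 against 55, 87 against 85). Against continuity-corrected Wald, it differs by about 0.6 points. The lower limits in Steps 1 and 2 are all above 50%.

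**Step 5: the denominator.** Participation is a share of eligible families; the 36 have already agreed and been randomized. The number approached is not fixed in the plan, so a range is shown under plain Wald at 70%:

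- Assumption: the 36 are the 70% who agreed. Then 36/0.70 ≈ 51 approached, giving 57.4-82.6%.
- Assumption: all of the roughly 400 patients to be screened (Section 4.1) are approached, giving 65.5-74.5%.

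Both are narrower than the printed interval.

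**The case against.** The strongest reply is that 53-87% can be obtained at n=36, at 95% and with ordinary rounding. A continuity correction combined with a t quantile or n−1 variance does it, and each component is a textbook device. This stands. A reader might infer that no standard method yields the figure, or that it is a proven arithmetic error. The documents do not support either, because they do not say how it was calculated. What can be said is that no single usual method reproduces it and that the combination needed is not described.

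A reader might also infer that the interval was computed for 27 to 29 participants, so that 7 to 9 of the 36 are unaccounted for, perhaps because 27 is 75% of 36 and 75% is the completion benchmark. That inference requires plain Wald, which the plan does not name, and an attrition allowance, which the plan does not mention. The study summary and Sections 4.1, 4.3 and 12 all give 36. A smaller evaluable number is one possible explanation and no more.

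Finally, it can be said that nothing depends on the figure. This largely stands. The sample size is expressly not power-based, the success rule as written applies to the percentage agreeing and does not mention the interval, and the printed interval is wider than Wald and so understates precision. It makes the point minor, but it does not make the sentence reproducible.

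**Conclusion.** The point holds as a minor one. With n=36, 70% and a 95% level, the usual methods give 55-85% (Wald), 54-86% (continuity-corrected Wald), 52-84% (exact, 25/36) or 53-82% (Wilson, 25/36). The stated 53-87% needs an unstated combination of adjustments, an unstated smaller n or an unstated higher level. Against Wald it is about 2 points too wide at each limit, and the comparison with the 50% benchmark is the same either way.

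This rests on applying the 95% level from the Aim 1 analysis to the precision sentence, and on reading its sample size as the 36 named just before it. A separate limit remains whichever formula was used: an interval on 36 randomized children does not describe precision for participation, which the plan measures among eligible families.

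**What to change.** Rewrite the precision sentence so that it gives n, level and method. Either of these would do:

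- for a proportion of 70% among the 36 randomized, 95% CI 55-85% (Wald, n=36); or
- for 25 of 36 randomized (69%), 95% CI 52-84% (exact).

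Label the figure as precision for a proportion among the 36 randomized, such as completion of the measurement time points, and not as precision for participation.

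For participation, add an interval computed on the expected number of eligible families approached, and state that number as an assumption. With about 51 approached, the Wald interval is about 57-83%.

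If 53-87% was calculated for a smaller evaluable number, or with combined adjustments at n=36, say which and keep the figure with that explanation.

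The cost is an edit to one paragraph. Sample size, feasibility rule, conduct and data collection do not change.
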